Contrast-enhanced magnetic resonance imaging (CE-MRI) is the standard imaging modality used to assess response to TACE by evaluating residual blood flow within the tumor [Brown et al. 2012; Hammerstingl et al. 2008; Akai et al. 2011]. The Society of Interventional Radiology guidelines recommend imaging follow-up four weeks post treatment [Brown et al. 2012]. A lack of arterial phase enhancement is used to indicate the lack of residual tumoral blood flow due to complete embolization and tumor necrosis. This one month time point has been adopted based on experience with the use of Lipiodol and on follow-up with contrast-enhanced computed tomography (CECT) scans; the non-tumor bearing liver requires 3-4 weeks to eliminate the Lipiodol by Kupffer cell phagocytosis [Brown et al. 2012]. In CE-MRI, the use of low molecular weight and water soluble contrast agents renders it difficult to differentiate granulation tissue and residual tumor perfusion and to differentiate peripheral viable tumors from inflammatory peritumoral infiltration if scanned within four weeks of treatment [Yan et al. 2002]. Differentiation between viable tumor and inflammation can be made in some cases by evaluating enhancement washout kinetics. Nevertheless, the cost of imaging and difficulty of inflammation in many cases has resulted in follow-up imaging recommendation to remain at 1 month [Brown et al. 2012]. CECT is used in patients in whom MRI is contraindicated. Confluent, dense Lipiodol uptake within treated tumors correlates with complete tumor necrosis, but may mask some residual tumor perfusion on CECT [Imaeda et al. 1993; Ito et al. 1995]. Following imaging, TACE or alternative treatment is repeated until a complete lack of arterial enhancement is achieved, after which tumoral response (evaluated by modified response evaluation criteria in solid tumors (mRECIST)) is assessed at 3-6 month intervals.

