reader. Studies will be presented in random order. The second round reads will be performed at least one month after the first. Outcomes will be defined as incompletely treated (i.e. requiring retreatment) based on (in order of preference of reference standard): a) pathological examination of explanted livers demonstrating live tumors; b) tumor enhancement seen with CT or MR and confirmed via angiography during retreatment; c) tumor growth on 6 month follow-up CE-CT/MRI; or d) asymmetrical or nodular tumor enhancement on CE-MRI/CT on 6 month follow-up. Incomplete treatment on CEUS (2D or 4D) will be evaluated by each reader and evidenced by the tumor showing either residual blood flow after treatment or nodular peripheral blood flow.

For questions 1-2, sensitivity (the ability to detect patients in need of retreatment) and specificity (the ability to identify patients who do not require retreatment) will first be calculated on a reader by reader basis. Four 2 x 2 tables will be constructed comparing the need for re-treatment based on the clinical gold standard described above and CEUS, tabulating true positives, false positives, false negatives, and true negatives. A table will be created for CEUS at 1-2 weeks and 1 month for both 2D and 4D CEUS and used to calculate sensitivity, specificity, accuracy, positive predictive value, and negative predictive value. Statistical significance between the reference standard and each of the 4 CEUS groups will be determined using a McNemar test. These values will also be calculated based on the majority decision (i.e. 4 or more readers in agreement). In the event of discordant readings during this analysis, tumor outcome will be decided by consensus by the two readers at TJU. Differences between techniques (2D vs. 4D) and time points (1-2 weeks vs. 1 month post treatment) will be determined by comparing areas under the receiver operating characteristic curves for each modality/time point based on necessity of tumor retreatment. Intra-rater and inter-rater variability will be calculated using a Shrout and Fleiss Interclass Correlation [Shrout and Fleiss 1979]. Finally, a logistical regression and analysis of variance will be performed to determine if significant variations exist between individual sites (to determine operator dependence), lesion size (tumor size dependency) or between patients treated with cTACE vs. DEB-TACE (treatment dependency).

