7.2.1 Sample Size Justification

As the most clinically important aims, aims 1-2 will be used as the basis for the sample size analysis, where each patient represents an independent data point used to evaluate the technique's sensitivity and specificity at both 1-2 weeks and 1 month follow-up times. Based on our pilot studies using 2D CEUS to evaluate TACE performed using Lipiodol [Kono et al. 2007] or drug-eluting-beads [Shaw et al. 2014], we expect to encounter a patient population in which up to 67% of patients require retreatment. A sample size analysis was performed using a binomial test with One-Sample Sensitivity and Specificity Analysis in NCSS/PASS 2008 (NCSS, East Kaysville, UT) to estimate the number of cases required to produce a over 85% power for this study. This analysis assumes sensitivity and specificities of 98%, an alpha of 0.05, prevalence of disease of 66.7%, and null sensitivity and specificities of 90%. Results from this analysis are provided in tabular format below.

Preva- ---- Power ----		Sample	--- Sensitivity ---		--- Specificity ---		----- Alpha -----			P
Size	H0 Sens. Spec.	H1 N1 and N	H0 Se0	H1 Se1	Sp0	Sens. Sp1	Spec. Target	lence Actual	Actual	P
0.0000	0.0000	7								
10	0.9000	0.9800	0.9000	0.9800	0.0500	0.0000	0.0000	0.6670		
0.0000	0.0000	13								
20	0.9000	0.9800	0.9000	0.9800	0.0500	0.0000	0.0000	0.6670		
0.0000	0.0000	20								
30	0.9000	0.9800	0.9000	0.9800	0.0500	0.0000	0.0000	0.6670		
0.0000	0.0000	27								
40	0.9000	0.9800	0.9000	0.9800	0.0500	0.0000	0.0000	0.6670		
0.5134	0.0000	33								
50	0.9000	0.9800	0.9000	0.9800	0.0500	0.0309	0.0000	0.6670		
0.4457	0.0000	40								
60	0.9000	0.9800	0.9000	0.9800	0.0500	0.0148	0.0000	0.6670		
0.7581	0.0000	47								
70	0.9000	0.9800	0.9000	0.9800	0.0500	0.0440	0.0000	0.6670		
0.7135	0.0000	53								
80	0.9000	0.9800	0.9000	0.9800	0.0500	0.0259	0.0000	0.6670		
0.6619	0.5455	60								
90	0.9000	0.9800	0.9000	0.9800	0.0500	0.0138	0.0424	0.6670		
0.8494	0.5134	67								
100	0.9000	0.9800	0.9000	0.9800	0.0500	0.0307	0.0309	0.6670		
0.8202	0.4735	73								
110	0.9000	0.9800	0.9000	0.9800	0.0500	0.0190	0.0203	0.6670		
0.9231	0.4457	80								
120	0.9000	0.9800	0.9000	0.9800	0.0500	0.0353	0.0148	0.6670		
0.9027	0.4195	87								
130	0.9000	0.9800	0.9000	0.9800	0.0500	0.0211	0.0108	0.6670		
0.9608	0.7581	93								
140	0.9000	0.9800	0.9000	0.9800	0.0500	0.0382	0.0440	0.6670		

0.9492	0.7358	100							
150	0.9000	0.9800	0.9000	0.9800	0.0500	0.0237	0.0338	0.6670	

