0.9791	0.7135	107							
160	0.9000	0.9800	0.9000	0.9800	0.0500	0.0374	0.0259	0.6670	
0.9735	0.6839	113							
170	0.9000	0.9800	0.9000	0.9800	0.0500	0.0255	0.0181	0.6670	
0.9893	0.6619	120							
180	0.9000	0.9800	0.9000	0.9800	0.0500	0.0382	0.0138	0.6670	
0.9857	0.8879	127							
190	0.9000	0.9800	0.9000	0.9800	0.0500	0.0250	0.0421	0.6670	
0.9945	0.8494	133							
200	0.9000	0.9800	0.9000	0.9800	0.0500	0.0385	0.0307	0.6670	

A total of 201 patients will be used in the final analysis for this study (the first 9 will be used as training cases and excluded), of which 135 (66.7%) will require retreatment. A total sample size of 201 (which includes 133 subjects with the disease) achieves 99% power to reject the null hypothesis for sensitivity, and 85% power to reject the null hypothesis for specificity.

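### CT and MRI count alike in the reference standard, yet Lipiodol may hide residual flow on CT: correct CEUS positives in CT-referenced cTACE lesions may be scored as false positives

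*Combined protocol and SAP*

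**What the plan says.** Section 7.2 (repeated in the Synopsis and in section 6.5) ranks four ways in which a lesion can be classed as incompletely treated: (a) viable tumour in the explanted liver; (b) enhancement on CT or MR, confirmed by angiography at retreatment; (c) growth at six months on CT or MRI; and "d) asymmetrical or nodular tumor enhancement on CE-MRI/CT on 6 month follow-up". In tiers b to d the two modalities are alternatives. No rule says which decides if both were done, and no analysis by modality is planned.

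Section 1.1 describes Lipiodol as part of cTACE, describes DEB-TACE without it, and says of CT: "Confluent, dense Lipiodol uptake within treated tumors correlates with complete tumor necrosis, but may mask some residual tumor perfusion on CECT". It also says Lipiodol in the lesion does not interfere with ultrasound. On when CT is used: "CECT is used in patients in whom MRI is contraindicated".

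Section 7.2 plans a logistic regression and analysis of variance to look for differences "between patients treated with cTACE vs. DEB-TACE (treatment dependency"). No term for reference modality is mentioned.

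Section 7.2.1 bases the sample size on a "binomial test with One-Sample Sensitivity and Specificity Analysis in NCSS/PASS 2008". It reports 99% power for sensitivity and "85% power to reject the null hypothesis for specificity".

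**The concern.** The protocol names a weakness of one reference test, ties it to one of the two treatments, and says the index test does not share it. The index test is then scored against that reference with nothing to separate the source of the reference result.

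The error has a direction. If CT misses residual flow that CEUS sees, the lesion is labelled completely treated and the CEUS reading becomes a false positive. Specificity falls; expected sensitivity does not, as long as the mislabelled lesions are typical of the diseased group in how CEUS reads them. Only Lipiodol-treated lesions are exposed, so an apparent cTACE versus DEB-TACE difference could arise even if CEUS were equally accurate after both.

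Two results are at stake: the specificity test, which is the less well powered of the two primary tests, and the reading of the treatment comparison.

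**Working it through.** **Inputs from section 7.2.1.** "This analysis assumes sensitivity and specificities of 98%, an alpha of 0.05, prevalence of disease of 66.7%, and null sensitivity and specificities of 90" per cent; 201 patients analysed. 66.7% of 201 is 134 diseased, leaving 67 true negatives. The section itself gives both 135 and 133 diseased; this does not matter here.

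**Reproducing the plan's power.** Exact one-sided binomial test: take the smallest cut-off r with P(X ≥ r | 0.90) ≤ 0.05; power is P(X ≥ r | 0.98).
- Sensitivity, n = 133: r = 126, actual alpha 0.0385, power 0.9945.
- Specificity, n = 67: r = 65, actual alpha 0.0307, power 0.8494.

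Both match the plan's table to four decimals. The specificity test tolerates only two false positives among 67.

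**Effect of k mislabelled lesions.** Suppose k truly residual lesions are masked on CT and never otherwise caught. They join the reference-negative group, and CEUS still reads 98% of them as positive.

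Apparent specificity = (0.98 × 67 + 0.02 × k) / (67 + k).

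Power comes from the sum of Bin(67, 0.98) and Bin(k, 0.02), with the cut-off for n = 67 + k. For k = 1 to 3 that cut-off still allows only two false positives.

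| k | Share of 134 diseased | Apparent specificity | Power |
|---|---|---|---|
| 0 | 0% | 98.0% | 84.9% |
| 1 | 0.7% | 96.6% | 61.6% |
| 2 | 1.5% | 95.2% | 27.2% |
| 3 | 2.2% | 93.9% | 1.6% |

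Check for k = 1: power = 0.98 × P(at most 1 false positive in 67) + 0.02 × P(at most 2) = 0.98 × 0.6115 + 0.02 × 0.8494 = 0.616.

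Apparent specificity reaches the 90% null at k = (0.98 − 0.90) × 67 / (0.90 − 0.02) = 6.1 lesions, or 4.5% of the diseased.

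**How large k might be.** The documents give no cTACE share, no CT share, no masking rate and no duration of masking inside the tumour. The shares below are assumptions: cTACE / CT within cTACE / masked and never otherwise caught. Then k = 134 × the product of the three.

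| Assumed shares | k | Overall specificity | cTACE | DEB-TACE |
|---|---|---|---|---|
| 25% / 10% / 5% | 0.2 | 97.8% | 97.0% | 98% |
| 50% / 25% / 10% | 1.7 | 95.7% | 93.4% | 98% |
| 50% / 50% / 25% | 8.4 | 87.3% | 78.8% | 98% |

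The cTACE column applies the same formula with 67 replaced by 67 × the cTACE share.

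**Random rather than fixed k.** Assume half the patients have cTACE and 2%, 4% or 5% of cTACE residual tumours are mislabelled (1.3, 2.7 or 3.4 lesions expected). Treating every reference-negative lesion as one draw at the blended specificity of 96.1%, 94.3% or 93.4% (n = 68, 70, 70) gives power of about 50%, 23% or 15%. This is milder than a fixed count of three, but still a large loss.

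**The case against.** A reader might infer that Lipiodol does hide residual flow, that CT stands level with MRI throughout the trial, and that specificity is therefore biased downward. The documents do not support that.

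- Section 1.1 says only that masking may occur and affects some perfusion; the same sentence links dense uptake to complete necrosis.
- CT is the fallback when MRI is contraindicated. Sections 3 and 6.7.1 name MRI alone for the one-month scan, so the CT share may be small.
- Explant pathology, and six-month growth, which does not depend on enhancement, can each reclassify a masked lesion.
- The three-to-four-week Lipiodol clearance concerns liver without tumour. Nothing says that masking inside the tumour persists to six months.
- The Rationale, and the Synopsis statement on the IND, speak of drug-eluting beads, so the cTACE share may be below half.
- The treatment comparison is secondary to the powered questions.

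All of this stands, and it is why the effect may be negligible. It does not remove the problem. Tier b cannot rescue a masked lesion, because angiography confirms only enhancement already seen. Tiers a and c cover only some lesions. The tiers define incomplete treatment only, so a lesion meeting none is apparently counted as completely treated. Without the modality on record, nobody could tell afterwards which end of the range applied.

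**Conclusion.** The concern holds as a possibility confined to one subgroup: cTACE lesions whose reference rests on CT alone and which neither explant nor six-month growth reclassifies. In these, a correct CEUS positive may be counted as a false positive. The direction (lower specificity, cTACE only) follows from the protocol's own statements; the size does not. It runs from about 0.2 lesions to about 8 under the assumed shares, all of which lie outside the documents.

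The test leaves little slack: given true sensitivity and specificity of 98% and 67 true negatives, one or two mislabelled lesions reduce power from 85% to about 62% or 27%. This is an inexpensive improvement worth making, not a demonstrated bias.

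**What to change.** 1. Record for each lesion the follow-up imaging modality (MRI or CT) and the reference tier that decided its status.
2. Where both scans exist, let MRI decide the enhancement criteria. This will help few lesions, since most patients on CT are there because they cannot have MRI.
3. Keep the four primary tables. Beside them, pre-specify sensitivity and specificity without any cTACE lesion whose reference rests on CT alone, reference-positive and reference-negative alike. Dropping only the negatives would alter prevalence and distort the predictive values and accuracy.
4. Repeat the cTACE versus DEB-TACE comparison on the same restricted set, or adjusted for modality (MRI versus CT). Do not adjust for reference tier: angiography occurs only among reference-positive lesions, so tier partly encodes the outcome.
5. Reconcile the CT-or-MRI wording of section 7.2 with the MRI-only completion criterion in section 6.7.1.

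The cost is two recorded variables and some SAP text, with no new imaging. The supportive analyses have fewer reference-negative lesions: specificity power would be 66.2% with 60 negatives, against 84.9% with 67. Because the exact test moves in steps, 63 gives 86.8% and 53 gives 71.4%. They should be read as supportive only.

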7.2 Statistical Analyses

Data analysis from this multi-center clinical trial will be performed to characterize 2D and 4D CEUS as a follow-up imaging tool for the evaluation of residual tumoral blood flow in patients with HCC treated with TACE.

Our statistical analysis will address three major questions:

1. Does 2D and 4D CEUS 1-2 weeks post TACE yield sensitivity and specificity greater than 90% for identifying residual tumor blood flow, thereby providing reliable earlier identification (relative to the current clinical standard) of patients in need of retreatment?
2. Does 2D and 4D CEUS 1 month post TACE yield sensitivity and specificity greater than 90% for identifying residual tumor blood flow, thereby providing an accurate, safe, and cost-effective imaging alternative for identifying TACE patients in need of retreatment?
3. Are quantifiable biomarkers generated by parametric imaging of 2D and 4D CEUS exams able to differentiate between fully treated and incompletely treated masses by measuring blood flow kinetics?

The first three cases at each institution will be used as reader training cases and will not be included in the final analysis. In the event of all cases showing identical response (i.e. all incompletely or completely treated), the first case with an alternative outcome will be substituted for the 9th case. Following reader training, each reader (all of whom have previous experience with CEUS and volumetric ultrasound) will be asked to evaluate all 201 remaining cases. 2D and 4D CEUS exams will be read separately and only after randomization. 2D cases will be viewed in a standard DICOM viewer, while 4D cases will be viewed in GE's 4D View software. Readers will first be asked to review both the patient's baseline CE-MRI/CT and CEUS exams to identify the size and location of the treated mass. Following baseline review, each reader will review the 1-2 week and 1 month CEUS exam (in random order). Intratumoral blood flow will be assessed as present or not present. Readers will then be asked to interpret the patient's 1 month follow-up CE-MRI/CT images and again evaluate the need to retreat based on residual blood flow. Finally, when available, readers will review subsequent CE-MRI/CT imaging studies (up to six months post TACE). MRI/CT evaluations will be based on mRECIST criteria. All imaging studies will be read twice by each

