For statistical question 3, all quantitative parameters will be compared between fully treated and incompletely treated masses using a Student's t-test. Additionally, lesions that demonstrate lack of residual enhancement at 1 month, but show recurrence at 6 month follow-up, will be compared to completely treated masses to determine if quantitative CEUS parameters can detect this lower level of residual disease. Statistical analysis will be performed with assistance from the biostatistician co-investigator using Stata 12.0 (Stata Corp, College Station, TX) with p values < 0.05 considered statistically significant after a Bonferroni-type adjustment for multiple tests. These statistical tests will answer our three major questions regarding the sensitivity and specificity of 2D and 4D CEUS as an imaging tool for the follow-up of TACE

at 1-2 weeks and 1 month (specific aims 1-2), as well as the influence of operator, reader, tumor size, and embolization material.

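### The binomial test against 90% that sizes the trial is missing from the analysis text, and the test named there, McNemar, has no 90% threshold

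*Combined protocol and SAP*

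**What the plan says.** Section 7.2 poses the first primary question as: "Does 2D and 4D CEUS 1-2 weeks post TACE yield sensitivity and specificity greater than 90% for identifying residual tumor blood flow". Question 2 asks the same at 1 month.

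Section 7.2.1 bases the sample size on these questions: "A sample size analysis was performed using a binomial test with One-Sample Sensitivity and Specificity Analysis". The null is 90%, the alternative 98%, alpha 0.05 and prevalence 66.7%. It concludes that 201 patients "achieves 99% power to reject the null hypothesis for sensitivity, and 85% power to reject the null hypothesis for specificity".

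For questions 1 and 2, section 7.2 builds four 2 x 2 tables (2D and 4D, at 1-2 weeks and 1 month) and derives sensitivity, specificity, accuracy and predictive values from each. The one significance test it names on these tables is: "Statistical significance between the reference standard and each of the 4 CEUS groups will be determined using a McNemar test". The Statistical Methodology part of the synopsis says the same. The other listed methods are a comparison of ROC areas between modalities and time points, intraclass correlation, regression and analysis of variance for site, lesion size and type of TACE, and a t-test for question 3.

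Section 7.2 closes with "These statistical tests will answer our three major questions regarding the sensitivity and specificity of 2D and 4D CEUS", and requires p-values below 0.05 to be "considered statistically significant after a Bonferroni-type adjustment for multiple tests".

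**The concern.** Against a reference standard, McNemar tests whether CEUS calls as many patients positive as the reference does, that is, whether false negatives equal false positives. It can be non-significant when CEUS is poor and its errors balance, and significant when CEUS is good and its few errors fall on one side. Neither result says whether sensitivity or specificity exceeds 90%.

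This is the primary objective. Followed as written, the p-values for questions 1 and 2 do not bear on the 90% target, and the quoted power belongs to a test that the analysis text does not name.

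A reader who infers the binomial test from 7.2.1 still does not know what it applies to. The plan calculates results reader by reader and by majority decision, and every study is read twice. Nor is it stated whether the Bonferroni-type adjustment covers the test. Those choices could then be made after the data are seen.

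**Working it through.** **Inputs.** Null 0.90, alternative 0.98, alpha 0.05, prevalence 66.7% and N = 201, all from 7.2.1. That section gives both 135 and 133 patients with disease; 201 x 0.667 = 134, leaving 67 without. I use 134 and 67 and show the range for 133 to 135. Neither the sidedness of the binomial test nor the version of either test is stated.

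**Step 1: reproduce the plan's power.** Take the smallest r with P(X >= r | n, 0.90) <= 0.05; power is P(X >= r | n, 0.98).
- n = 133: r = 126, actual alpha 0.0385, power 0.9945.
- n = 67: r = 65, actual alpha 0.0307, power 0.8494.

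Both match the table row for N = 200 to four decimals. An upper tail of 0.025 gives 0.982 and 0.6115, which do not match. The sizing test is therefore an exact binomial test at one-sided 0.05.

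**Step 2: McNemar on example tables (134/67).** Exact two-sided p = min(1, 2 x P(X <= min(FN, FP))), with X ~ Bin(FN + FP, 0.5).
- FN = 20, FP = 20: sensitivity 114/134 = 85%, specificity 47/67 = 70%. McNemar p = 1.00, although both are well below target.
- FN = 6, FP = 0: sensitivity 128/134 = 95.5%, specificity 67/67 = 100%. McNemar p = 2 x 0.5^6 = 0.031, flagging a difference from the reference. The unadjusted binomial tests reject 90% for both (p = 0.016 and 0.0009). At 0.05/4 = 0.0125, neither the McNemar result nor the sensitivity result would be significant.

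**Step 3: rejection rates.** These sum over all values of FN ~ Bin(134, 1 - Se) and FP ~ Bin(67, 1 - Sp). The binomial column requires both tests to reject at 0.05 and is the product of the two probabilities, since they use different patients.

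| True Se/Sp | Exact McNemar, 0.05 | Exact McNemar, 0.0125 | Both binomial tests, 0.05 |
|---|---|---|---|
| 98%/98% | 1.6% | 0.2% | 84% |
| 80%/60% | 1.3% | 0.2% | 0% |
| 90%/90% | 23% | 9.5% | 0.1% |
| 80%/80% | 51% | 28% | 0% |
| 80%/90% | 95% | 85% | 0% |

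The 80%/60% row is a point where expected errors balance: 134 x 0.20 = 26.8 and 67 x 0.40 = 26.8. McNemar barely separates it from the design alternative. The uncorrected chi-square version gives 8.1% at 98%/98% and 1.9% at 80%/60% (133/67 patients), so the conclusion does not depend on the version.

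**Step 4: the binomial test under the adjustment (numbers of tests assumed).** Power at 98%, with 134 and 67 patients:

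| Per-test alpha | Critical values | Sensitivity | Specificity | Both |
|---|---|---|---|---|
| 0.05 | 127/134, 65/67 | 0.994 | 0.849 | 0.84 |
| 0.05/4 = 0.0125 | 129/134, 66/67 | 0.947 | 0.611 | 0.58 |
| 0.05/8 = 0.00625 | 129/134, 67/67 | 0.947 | 0.258 | 0.24 |

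In the last row all 67 must be correct, so specificity power is 0.98^67 = 0.258. With 133 to 135 diseased patients, specificity power is 0.60 to 0.62 for four tests and 0.25 to 0.26 for eight.

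**The case against.** The strongest reply is that 7.2.1 is a subsection of the statistical analysis section and already names the test, the null and the alpha for these questions, so the hypothesis can be recovered. Nor does the plan say in so many words that McNemar decides the 90% question. Sensitivity and specificity will be reported from every table, so 85% and 70% would be visibly short of target whatever McNemar shows. The introduction also speaks of estimating them within an adequate confidence interval.

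Part of this stands. The 90% hypothesis is in the document, and the test can be inferred. But a sample size section does not define the analysis. The analysis text names a different test on those tables and then says that the listed tests answer the questions. A point estimate carries no inference about 90%, and the introduction gives no interval method.

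It is also fair that the multiplicity loss is conditional, because the scope of the adjustment is not stated. The eight-test case arises only if sensitivity and specificity are counted as separate tests. Finally, 134/67 is a best case at 1-2 weeks, since patients who miss that exam stay in the study.

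**Conclusion.** The concern holds and needs correcting before analysis, because it affects the primary objective. As written, no named test, interval or success rule addresses whether sensitivity and specificity exceed 90%, and McNemar does not track that target: it rejects 1.6% of the time at 98%/98%, 1.3% at 80%/60% and 95% at 80%/90%. The 99% and 85% power are correct for a one-sided exact binomial test at an unadjusted 0.05, which the analysis text omits.

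If the adjustment covers that test, specificity power falls to 0.61 for four tests or 0.26 for eight. These figures assume 134 and 67 evaluable patients, one result per patient, the exact versions of both tests and the stated numbers of tests. The mismatch between McNemar and the 90% target depends on none of them.

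**What to change.** In 7.2 and the synopsis:

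- Make the significance test for questions 1 and 2 the one-sided exact binomial test against 0.90 that reproduces the 7.2.1 table, or the matching exact lower confidence bound. State the sidedness.
- Apply it to sensitivity in reference-positive patients and to specificity in reference-negative patients, for each modality and time point. Require both nulls to be rejected before claiming performance above 90%.
- Name the single result tested. One option is the majority decision from the first reading round, with reader-by-reader results as supporting; 7.2 defines the majority but not the round. Say whether the two-reader consensus for discordant readings is part of that result, and how a patient with two imaged lesions counts.
- State how the Bonferroni-type adjustment applies. If both nulls must be rejected within a claim, no split between sensitivity and specificity is needed, so the divisor is at most four (2 modalities x 2 time points).
- If the adjustment covers these tests, restate the power in 7.2.1.
- Keep McNemar, if wanted, as a secondary check for systematic over- or under-calling.

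The cost is protocol and SAP wording, plus a revised power statement if the adjustment applies. No new data are needed.

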6.5 Efficacy Assessments

Following reader training, each reader (all of whom have previous experience with CEUS and volumetric ultrasound) will be asked to evaluate all 201 remaining cases. 2D and 4D CEUS exams will be read separately and only after randomization. Readers will first be asked to review both the patient's baseline CE-MRI/CT and CEUS exams to identify the size and location of the treated mass. Following baseline review, each reader will review the 1-2 week and 1 month CEUS exam (in random order). Intratumoral blood flow will be assessed as present or not present. Readers will then be asked to interpret the patient's 1 month follow-up CE-MRI/CT images and again evaluate the need to retreat based on residual blood flow. Finally, when available, readers will review subsequent CE-MRI/CT imaging studies (up to six months post TACE). MRI/CT evaluations will be based on mRECIST criteria. All imaging studies will be read twice by each reader. Studies will be presented in random order. The second round reads will be

performed at least one month after the first. Outcomes will be defined as incompletely treated (i.e. requiring retreatment) based on (in order of preference of reference standard): a) pathological examination of explanted livers demonstrating live tumors; b) tumor enhancement seen with CT or MR and confirmed via angiography during retreatment; c) tumor growth on 6 month follow-up CE-CT/MRI; or d) asymmetrical or nodular tumor enhancement on CE-MRI/CT on 6 month follow-up. Incomplete treatment on CEUS (2D or 4D) will be evaluated by each reader and evidenced by the tumor showing either residual blood flow after treatment or nodular peripheral blood flow.

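### Section 7.2 does not say which read answers the 90% questions, and a majority read can exceed 90% when no single reader does

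*Combined protocol and SAP*

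**What the plan says.** Questions 1 and 2 in section 7.2 are yes/no questions: whether 2D and 4D CEUS, at 1-2 weeks and at 1 month, "yield sensitivity and specificity greater than 90% for identifying residual tumor blood flow".

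The results that could answer them are described in the same section and repeated in the synopsis:

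- Sensitivity and specificity "will first be calculated on a reader by reader basis".
- The layout of the results is then given: "Four 2 x 2 tables will be constructed comparing the need for re-treatment", one for each modality and time point. Whose calls fill them is not stated.
- A vote is added: "These values will also be calculated based on the majority decision (i.e. 4 or more readers in agreement".
- Where that vote is not clear-cut, the two TJU readers agree the call between them.
- Section 6.5 adds: "All imaging studies will be read twice by each reader". Neither section says which round enters the tables.

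The test named for these tables is McNemar's, comparing CEUS with the reference standard. P values are judged after a Bonferroni-type adjustment, with no count of tests and no mention of readers. The sample size in section 7.2.1 rests on a one-sample binomial test of 90% against 98% in which "each patient represents an independent data point used to evaluate the technique's sensitivity and specificity". It does not say which read supplies that data point.

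**The concern.** Several readers, two rounds and a vote give several answers to one yes/no question. With six readers, each modality and time point would have 6 x 2 = 12 single-reader results plus one majority result per round, 14 in all. No rule picks one, says how many readers must pass, or pools readers with a variance reflecting that they all read the same patients.

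These results estimate different things. A single-reader table estimates what one reader achieves. A majority table estimates what a panel achieves, and a panel normally does better because isolated errors are outvoted. The protocol presents CEUS as an imaging alternative to MRI/CT and nowhere proposes reading by vote in practice. If the panel figure were reported as the answer, it could support a claim above 90% that no individual reader meets. If every reader had to pass, a good technique could fail. Without a written rule, the choice can be made after the results are known.

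**Working it through.** **Inputs from the documents.** Null 0.90, alternative 0.98, alpha 0.05 (sidedness not stated), prevalence 0.667, 201 patients analysed (section 7.2.1); majority of 4 or more readers, with the two TJU readers settling discordance (section 7.2).

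**Inputs that are assumptions.** Six readers (4 is a bare majority of 6 or 7); equal accuracy p for all readers; discordance means a 3-3 tie; half of ties resolved correctly; a range of between-reader error correlation. The documents give none of these.

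**Step 1: the plan's own power.** Take the smallest r with P(X >= r | n, 0.90) <= 0.05, one-sided; power is P(X >= r | n, 0.98).

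- n = 133: r = 126, alpha 0.0385, power 0.9945.
- n = 67: r = 65, alpha 0.0307, power 0.8494.

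Both match the plan's table row for 200 patients. A two-sided 0.05 would give specificity power 0.6115, so the plan's test is one-sided. For 201 patients, 0.667 x 201 = 134 need retreatment and 67 do not (the text gives both 135 and 133; this barely matters). At n = 134, r = 127 and alpha is 0.0364.

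**Step 2: panel accuracy.** Let a case effect z ~ N(0,1) make some cases harder for everyone, with latent correlation rho:

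p(z) = Phi[(Phi^-1(p) + sqrt(rho) z) / sqrt(1 - rho)]

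Panel accuracy = E_z[ P(Bin(6, p(z)) >= 4) + 0.5 P(Bin(6, p(z)) = 3) ]

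With independent errors and p = 0.90: 0.98415 + 0.5 x 0.01458 = 0.991.

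**Step 3: pass rates with every reader exactly at 90%.** The panel accuracy is put into the step 1 tests (127/134 and 65/67). The two groups contain different patients, so the joint rate is the product.

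| Latent rho | Error correlation | Panel accuracy | Sensitivity passes | Specificity passes | Both pass |
|---|---|---|---|---|---|
| 0 | 0 | 99.1% | 100% | 98% | 98% |
| 0.4 | 0.19 | 95.5% | 74% | 41% | 0.741 x 0.413 = 31% |
| 0.6 | 0.32 | 93.5% | 36% | 18% | 0.356 x 0.183 = 6.5% |
| 0.8 | 0.51 | 91.7% | 12% | 7.5% | 0.123 x 0.075 = 1% |
| 0.9 | 0.65 | 90.8% | 6.8% | 4.8% | 0.068 x 0.048 = 0.3% |
| Single reader | - | 90% | 3.6% | 3.1% | 0.036 x 0.031 = 0.1% |

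The joint column applies when sensitivity and specificity are both at 90%. If one is well above 90% and the other exactly at it, the joint rate moves towards the single rate for the one at 90%.

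**Step 4: readers below the threshold.** With every reader at 88% and latent rho 0.5, panel accuracy is 0.905 + 0.5 x 0.048 = 92.9%. The panel passes in 25% (sensitivity) and 13% (specificity) of trials; a single reader passes in 0.7% and 1.0%.

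**Step 5: what moves the result (readers at 90%).**

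- All ties resolved wrongly: 36% and 19% at latent 0.4, 12% and 7% at 0.6, about nominal at 0.8.
- Bonferroni over four tests (count assumed; alpha 0.0125, critical values 129/134 and 66/67): sensitivity 44% at latent 0.4 and 13% at 0.6; specificity 19% and 6%.
- Seven readers instead of six: at latent 0.5 the panel is at 95.0% rather than 94.5%.

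**Step 6: other unwritten rules.** If all six readers had to pass, specificity power at a true 98% would be 0.8494^6 = 38% for independent readers, and about 43-47% at latent 0.4 to 0.6. If any one of six independent readers at the null sufficed, the error would be 1 - (1 - 0.0364)^6 = 20% for sensitivity and 1 - (1 - 0.0307)^6 = 17% for specificity.

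**The case against.** The plan is not silent on readers. Reader-level values come first and the majority values are an addition, so the reader-level results would stand beside any panel figure. Intra- and inter-rater agreement is also planned. All of that stands, but it does not give one answer when several readers fall on both sides of 90%.

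A reader might infer that the sample size points to the panel, because it counts one data point per patient. The documents do not support this: one reader's first-round table for one modality and time point also has one call per patient. Nor do they support treating the majority as the natural answer, since the order of the text, if anything, puts the reader level first.

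The size of the effect is uncertain. The readers share training cases, are experienced in CEUS and view the same stored images, so high agreement is plausible, and at an error correlation of 0.65 the inflation nearly vanishes. The tie rule and the unspecified Bonferroni count also matter. These points limit the magnitude but do not supply the missing rule.

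Panel accuracy is a legitimate target if it is declared. It overstates accuracy only when the single reader is the target.

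**Conclusion.** The gap is real and should be fixed. No passage says which result answers questions 1 and 2, how readers are combined or which round counts, and the test named for the tables does not test 90%. This rests on the text alone.

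That a majority read can exceed 90% when no reader does is confirmed by calculation. Under the stated assumptions, the chance that the panel passes with every reader exactly at 90% runs from near certainty with independent errors to 12% (sensitivity) and 7.5% (specificity) at error correlation 0.51, and close to nominal beyond that. The joint rate falls from 98% to about 1% over the same range.

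A reader might conclude that the trial will report an inflated accuracy. The documents do not support that: they do not make the majority read the deciding one, and the correlation is unknown. The supported statement is that the plan leaves the choice open and that the choice can change the answer.

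**What to change.** State in section 7.2 and the synopsis, before any reads are analysed, that:

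1. Questions 1 and 2 are answered by first-round sensitivity and specificity averaged over readers, for each modality and time point.
2. Each is tested against 90% with a variance that reflects all readers reading the same patients (Obuchowski-Rockette, or a bootstrap resampling patients and readers), with the sidedness and the number of tests in the Bonferroni adjustment given.
3. The per-reader and majority tables are secondary, and the number of readers is stated.
4. Second-round reads are used only for intra-reader agreement.

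A named reader, or a stated number of readers who must each pass, would also close the gap. The average uses all first-round reads and fits the aim of studying reader dependence.

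The cost is wording and a standard analysis on reads already planned; no extra patients or reads are needed. The headline figure may be lower than the panel figure. The stated 99% and 85% power applies to one call per patient and should be labelled so. Power for the reader average depends on between-reader correlation, which the documents do not give, and has not been calculated here.
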